10.2 Demographics and Baseline Characteristics

Demographic parameters (age, sex, race, and ethnicity) and other baseline characteristics (body weight, body mass index (BMI), HIV status, CD4+ T-cell count (if HIV-positive), HR, DBP, SBP, current eye symptom, visual acuity impairment in one or both eyes, color vision deficiency in one or both eyes, log CFU on solid culture, TTP in liquid MGIT culture, and log concentration of sputum LAM, drug susceptibility testing for isoniazid and rifampicin, and minimum inhibitory concentrations (MIC) of TBA-7371) will be summarized by treatment group for all participants in the mITT and safety populations.

Continuous variables will be summarized using descriptive statistics (n, mean, standard deviation, and median, minimum, maximum). Categorical variables will be summarized using counts and percentages.

A data listing of demographics and baseline characteristics will be provided.

10.3 Treatment Exposure

For each participant in the safety population, duration of exposure to study drug will be calculated as (last dose date – first dose date + 1). Duration of exposure will be summarized as both continuous and categorical variables by treatment group. For categorical presentation, the frequency and percentage of participants in each of the following categories will be presented: ≤ 3 days, 4 to 6 days, 7 to 9 days, 10 to 13 and 14 days by treatment group.

A data listing of treatment exposure will be provided.

10.4 Protocol Deviations

A summary of the frequency and percentage of participants in the safety population with major protocol deviations for each deviation category will be provided by treatment group. A participant with multiple occurrences of a major protocol deviation in the same deviation category will only be counted once. A listing of protocol deviations by treatment group and participant will be provided.

11 EFFICACY PARAMETERS

11.1 Log CFU/mL Counts

11.1.1 Primary Analysis

CFU/mL counts are derived from CFU count per mL collected from the Middlebrook 7H11S plates of overnight sputum samples, where sputum is collected twice during the screening phase (Days -2 and -1) and daily on 14 consecutive days during the study treatment phase (Days 1 to 14). CFU/mL will be calculated as follows:

$$CFU/mL = \frac{\text{mean of two CFU plate counts}}{\text{dilution factor} \times 0.909 \times 0.2}$$

where 0.909 is a 10:1 dilution of sputum in sputasol and 0.2 mL is the volume on the plate.

The following rules and convention will apply for handling of the following categories:

- Contaminated or no result: The CFU/mL counts associated with contaminated or no result samples will be set to missing.
- Too numerous to count (TNTC ≥ 401 colonies): The CFU/mL counts associated with TNTC samples will be set to 401.
- CFU/mL counts < 5 : The CFU/mL counts will be set to 5.

The primary end-point will be the slope of the \log_{10} CFU/mL counts from Screening to Day 14 [BA_{CFU}(0-14)], i.e., average change in \log_{10} CFU/mL count per day over 14 days. The \log_{10} CFU/mL counts vs. time profiles over 14 days of treatment may be biphasic, i.e. the rate of change in log CFU changes over time. A simple solution (Diacon et al., 2013) is to characterize the participant-specific log CFU count vs. time profiles using a bilinear regression model, which has been proved to fit the data of many TB bactericidal agents quite well, especially over the time interval of 14 days.

The form of the bilinear regression model is given by:

$$\log_{10} CFU/mL = \alpha - \beta_1 \cdot t + \varepsilon; \quad t \leq \kappa;$$

$$\log_{10} CFU/mL = \alpha + (\beta_2 - \beta_1) \cdot \kappa - \beta_2 \cdot t + \varepsilon; \quad t > \kappa$$

where the parameters α and κ are the intercept and node parameter of the regression curve, respectively, the slopes β_1 and β_2 characterize the line of decline on or before the node ($t \leq \kappa$) and after the node ($t > \kappa$), respectively, and ε is the error term assumed to be independently distributed normally with mean zero and variance σ^2 . The parameters are constrained to aid in convergence as such: $\alpha > 0$, $1 < \kappa < 14$, $\sigma^2 > 0$, all $\in \mathbb{R}$. The SAS PROC NLMIXED procedure will be used to fit the bilinear regression model for individual participants in each treatment group. Suggested starting values for the parameters are $(\alpha, \beta_1, \beta_2, \kappa) = (6, 0, 0, 2)$ however a grid search approach can be followed to obtain sensible starting values. See SAS code in the Appendix which uses a grid search and picks the best fitting model.

If the bilinear regression model is selected, the average change in \log_{10} CFU/mL per day over 14 days will be estimated for each participant i by:

$$BA_{CFU}(0-14)_i = [\hat{\kappa}_i \hat{\beta}_{1i} + (14 - \hat{\kappa}_i) \hat{\beta}_{2i}] / 14$$

where $\hat{\beta}_{1i}$ is the estimated slope prior to the estimated inflection point $\hat{\kappa}_i$, and $\hat{\beta}_{2i}$ is the estimated slope after the estimated inflection point $\hat{\kappa}_i$. The parameters of main interest include the slopes $\hat{\beta}_{1i}$ and $\hat{\beta}_{2i}$, and the inflection points, $\hat{\kappa}_i$, and can be readily estimated using least squares. BA_{CFU}(0-14) can be estimated in PROC NLMIXED directly.

In the case where a subject does not have a non-missing measurement at Day 14, we have that

$$BA_{CFU}(0 - t_{last})_i = [\hat{\beta}_{1i} + (t_{last} - \hat{\kappa}_i) \hat{\beta}_{2i}] / t_{last}$$

where t_{last} is the last time point at which CFU was observed.

However, it is also likely that some of the participant specific \log_{10} CFU/mL count vs. time profiles will be better characterized using a simple linear regression model.

The form of the simple regression linear model is given by:

$$\log_{10} CFU/mL = \alpha - \beta_1 \cdot t + \varepsilon$$

where the parameters α and slope β_1 are the intercept and the slope that characterize the linear decline, and ε is the error term assumed to be independently distributed normally with mean zero and variance σ^2 . The SAS PROC NLMIXED procedure will also be used to fit a simple linear

regression model for individual participants in each treatment group in order to ensure the Akaike information criteria (AIC) values for the linear and bilinear models are based on the same form of the likelihood function. Suggested starting values for the parameters are $(\alpha, \beta_1) = (6, 0)$ however a grid search approach can be followed to obtain sensible starting values.

If the linear regression model is selected, the average change in $\log_{10}\text{CFU}/\text{mL}$ count per day over 14 days will be estimated by the constant linear regression slope estimate, $\hat{\beta}_{1i}$, i.e.

$$BA_{CFU}(0 - 14)_i = \hat{\beta}_{1i}.$$

Therefore, for each participant, slopes will be estimated using both bilinear and simple linear regression models, and the better fit model based on lower AIC will be selected for that participant and used to estimate $BA_{CFU}(0-14)$. The $\log_{10}\text{CFU}/\text{mL}$ screening measurement used in the model will be the average of the two individual screening measurements. $BA_{CFU}(0-14)$ will be calculated for each participant within a treatment group individually, and then used as the response variable in an ANCOVA model, with a fixed effect for treatment group and screening $\log_{10}\text{CFU}/\text{mL}$ count as a covariate. Treatment group means from the ANCOVA model will be used to quantify the evidence that each of the treatment group mean $BA_{CFU}(0-14)$ is less than 0 (i.e., that the treatment group mean has a negative slope on average). The mITT population will be used for the primary efficacy analysis with analyses using the per-protocol population performed to assess the robustness of results. The SAS PROC MIXED procedure will be used to fit an ANCOVA model.

Multiplicity will be handled by means of a step-down sequential approach. The five TBA-7371 treatment regimens will be divided into 3 testing groups: Group 1 = Cohort V (400 mg QD) and Cohort IV (100 TID); Group 2 = Cohort III (200 mg QD) and Cohort II (100 BID); and Group 3 = Cohort 1 (100 QD). Group 1, or the group with the highest cohort allowed by the IDMC will be tested first using a Holmberg multiplicity adjustment: if the maximum and minimum one-sided p-values are ≥ 0.05 and ≥ 0.025 , respectively, formal testing will be stopped and all cohorts below will be declared a failure; if the maximum and minimum one-sided p-values are ≥ 0.05 and < 0.025 , formal testing will be stopped but the regimen with p-value < 0.025 will be declared a success; if the maximum and minimum one-sided p-values are < 0.05 and < 0.025 , both cohorts will be declared a success and testing will proceed to Group 2 regimens with the same step-down approach to continue until a failed cohort is observed.

The study will be declared a success if at least one of the TBA-7371 treatment groups achieves a statistically significant 1-sided p-value and demonstrates an acceptable safety profile.

Geometric mean and geometric mean ratio of post-baseline to baseline of CFU/mL counts with 95% confidence interval (CI) at each time point will be presented in line plots by treatment group. In addition, observed and fitted lines of bilinear and linear regression models of $\log_{10}\text{CFU}/\text{mL}$ counts over time will be presented for each participant.

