6.2 Sample Size Determination

Anticipating all cohorts are to be assessed in the study, approximately 90 participants will be randomized in a 5:1 ratio to either TBA-7371 or control group, totaling N = 15 participants for each TBA-7371 treatment and control groups (receiving treatment with HRZE).

Bactericidal effect

Based on Diacon et al. (Diacon, 2013) standard deviations associated with BAcfu(0-14) were relatively consistent across 5 treatment groups, ranging from 0.05 to 0.08. If we assume conservatively that the true standard deviation of the BAcfu(0-14) measures for the TBA-7371 treatment groups is equal to 0.1, then with N = 15 per group we have 80% (90%) power to detect a true group mean BAcfu(0-14) reduction of 0.067 (0.079), using a 1-sided alpha = 5%. For reference, the observed BAcfu(0-14) reduction in Diacon et al, 2013 were 0.040, 0.056, 0.077, 0.104, and 0.122 for Bedaquiline 100 mg, 200 mg, 300 mg, 400 mg and standard HRZE, respectively.

Safety

With N = 15 per group, we have approximately 80% (90%) probability to observe at least one AE if the true AE rate is 10% (15%). We have only 54% probability to observe at least one AE if the true AE rate is 5%. Across the five TBA-7371 treatment groups (N=75), we have 90% probability to observe at least one AE if the true AE rate is 3.0%.

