11.1.3.1 ANCOVA model using average change from baseline

Given that treatment ends on Day 14, $BA_{CFU}(0-14)$ of $\log_{10}CFU/mL$ counts over 14 days of treatment will be estimated by calculating an average of the change from baseline to day 14 in log of CFU as follows:

$$BA_{CFU}(0-14)_i = \frac{\log_{10}(CFU/mL)_{14} - \log_{10}(CFU/mL)_{base}}{14}.$$

An ANCOVA model will be fitted as done in [Section 11.1.1](#). If the CFU is missing at Day 14, then the latest time point with a measurement with the corresponding denominator will be used, e.g. if the latest day with a CFU measurement is Day 10, then the divisor in the formula above will be 10.

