11.1.3.2 Random intercepts and slopes model across all data points

A mixed model with random intercepts and slopes will be fitted in order to estimate the average change from baseline to Day 14. It will use all log CFU data points for all participants and time points. The model is given by

$$\log_{10} CFU/mL = \alpha + u_i + (\beta_1 + b_i)t + \beta_{2j}X_{1j} + \beta_{3j}X_{1j}t + \beta_4X_{2i} + \varepsilon_{ij}$$

where $t = 0, 1, \dots, 14$, X_{1j} is the dummy indicator for treatments $j = 1, \dots, 5$ with HRZE as the reference group, X_{2i} the covariate for baseline $\log_{10}\text{CFU/mL}$, u_i the random intercepts with distribution $u_i \sim N(0, \sigma_u^2)$, b_i the random slopes with distribution $b_i \sim N(0, \sigma_b^2)$ and $\varepsilon_{ij} \sim N(0, \sigma^2)$. An unstructured covariance structure will be used for the variance-covariances of the random effects. It may be simplified to variance components (option “vc”) if the former doesn’t yield convergence or there is no gain in model fit as decided through the AIC. The fixed effects of the model are given by day t , treatment group X_j , baseline $\log_{10}\text{CFU/mL}$ and the interaction between time and treatment group.

The average slope over time for each treatment group will be estimated and reported with 90% confidence intervals using the time and interaction effects, i.e.

$$(\hat{\beta}_1 + \hat{\beta}_{3j}).$$

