13.3 Exposure-Response Analysis

The exposure-response E_{max} model will be used to estimate EC_{90} as follows:

$$BA_{CFU}(0-14) = \frac{E_{max} \cdot C_{max(ss)}}{EC_{50} + C_{max(ss)}} + \varepsilon$$

where:

- $BA_{CFU}(0-14)$ is the average change in log(CFU) counts over each day from screening to day 14.
- E_{max} is the maximal TBA-7371 EBA effect.
- EC_{50} is the expected concentration of TBA-7371 associated with 50% of E_{max} .
- $C_{max(ss)}$ is the steady state C_{max} of TBA-7371 measured at day 14.
- ε is a random error assumed to be normally distributed with mean zero and constant variance σ^2 .

Exposure-response analysis will be performed in the PK population with participants having PK data measured on day 14. The SAS PROC NLMIXED procedure will be used to fit an E_{max} model. Maximum likelihood estimates and corresponding 95% CIs for E_{max} and EC_{50} will be provided. The prediction of EC_{90} to reach 90% of E_{max} is computed as

$$EC_{90} = 9 \cdot EC_{50}$$

95% CI for the estimate of EC90 will be provided. An exposure-response curve of E_{max} model will be produced and vertical reference lines for EC₅₀ and EC₉₀ will be provided for each treatment group as well as overall.

Alternative sigmoid exposure-response model may be explored if deemed appropriate.

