Appendix 4 SAS Code

SAS code for computing 95% confidence interval for single proportion based on the mid-P method:

```
proc freq data=<dataset> order=freq;
  tables category / binomial (CL=MIDP) alpha=0.05;
  weight Count;
run;
```

SAS code for response-exposure E_{max} model:

```
ods output fitstatistics=<Data with aic>;
ods output parameterestimates=<Data with slope estimates>;
proc nlmixed data=<dataset>;
  by <treatment group>;
  parms Emax=<numeric>
    EC50=<numeric>
    s2=<numeric>;
  mu=(Emax*Cmax) / (EC50+Cmax);
  model <Avg. Slope(0-14)> ~ normal(mu,s2);
run;
```

SAS code for bilinear regression model with κ as one of the parameters:

```
ods output fitstatistics=<Data with aic>;
ods output parameterestimates=<Data with slope estimates>;
ods output additionalestimates=<Data with BA(0-14) estimate>;
run;
proc nlmixed data=<dataset>;
  by <subject ID>;
  parms alpha=4 to 8 by 0.5    betal=-0.3 to 0.3 by 0.05
beta2=-0.3 to 0.3 by 0.05    kappa=2 to 10 by 1    s2=0.05 to 0.3
by 0.05 / best=1;
  bounds alpha >0,    1 < kappa < 14,    s2>0; * Add constraints to
parameters to improve convergence;
  if day <= kappa then mu = alpha + betal*day;
  else if day > kappa then mu = alpha + betal*kappa +
beta2*(day-kappa);
  model logCFU ~ normal(mu,s2);
  estimate 'BACfu(0-14)' (kappa*betal + (t_last-
kappa)*beta2)/t_last; *Estimate BA(0-14);
run;
```

SAS code for bilinear regression model with kappa fixed at 2:

```
ods output fitstatistics=<Data with aic>;
ods output parameterestimates=<Data with slope estimates>;
proc nlmixed data=<dataset>;
  by <subject ID>;
  parms alpha=4 to 8 by 0.5    beta1=-0.3 to 0.3 by 0.05
beta2=-0.3 to 0.3 by 0.05 s2=0.05 to 0.3 by 0.05 / best=1;
  bounds alpha >0,    s2>0; * Add constraints to parameters to
improve convergence;
  if day <= 2 then mu = alpha + beta1*day;
  else if day > 2 then mu = alpha + beta1*2 + beta2*(day-2);
  model logCFU ~ normal(mu,s2);
run;
```

SAS code for simple regression model:

```
ods output fitstatistics=<Data with aic>;
ods output parameterestimates=<Data with slope estimates>;
proc nlmixed data=<dataset>;
  by <subject ID>;
  parms alpha=4 to 8 by 0.5    beta1=-0.3 to 0.3 by 0.05    s2=0.05
to 0.3 by 0.05 / best=1;
  mu = alpha + beta1*day;
  model logCFU ~ normal(mu,s2);
run;
```

SAS code for ANCOVA (lsmeans statement used to estimate 90% CIs, lsmestimate statements used for one-sided 5% p-values, trt = treatment group with HRZE as reference):

```
proc mixed data=<dataset>;

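### SAP 11.1.1 defines too-numerous-to-count as 401 or more colonies on the plate but enters 401 CFU/mL, so such a sample is analysed below its own lower bound

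*SAP*

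**What the plan says.** SAP 11.1.1 calculates CFU/mL as the mean of two plate counts divided by (dilution factor × 0.909 × 0.2), "where 0.909 is a 10:1 dilution of sputum in sputasol and 0.2 mL is the volume on the plate". It does not define the dilution factor or give its values.

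Three handling rules follow. Contaminated or no-result samples become missing. For crowded plates: "Too numerous to count (TNTC ≥ 401 colonies): The CFU/mL counts associated with TNTC samples will be set to 401". CFU/mL values under 5 become 5.

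The log10 of the resulting CFU/mL is the analysed variable:
- It is fitted per participant, linear or bilinear by AIC, to give BA_CFU(0-14).
- The log10 CFU/mL "screening measurement used in the model will be the average of the two individual screening measurements", and that screening value is also the ANCOVA covariate.
- BA_CFU(0-14), which "is the average change in log(CFU) counts over each day from screening to day 14", is the response in the exposure-response model (SAP 13.3).
- The random-slopes sensitivity analysis (SAP 11.1.3.2) takes the same values: "It will use all log CFU data points for all participants and time points".
- The average-change sensitivity analysis (SAP 11.1.3.1) uses the baseline and the last value: "If the CFU is missing at Day 14, then the latest time point with a measurement with the corresponding denominator will be used".

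Protocol 8.2.1 leaves sputum handling and testing to a laboratory instruction document. Neither the protocol nor the SAP states which dilutions are plated or how often too-numerous-to-count (TNTC) samples are expected.

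**The concern.** The rule mixes two scales. Its threshold is a number of colonies on a plate; its substitute is a concentration. Under the SAP's formula the two differ by a factor of at least 5.5, so the samples with the heaviest growth are given a value below the least they can contain. The order of samples is reversed as well: a plate that could be counted can score higher than one too crowded to count.

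The primary endpoint is a slope, so the error acts in opposite directions by day. A TNTC sample at screening or early in treatment hides a real fall. A TNTC sample late in treatment, as in a participant whose counts rise, creates a false one. The value is carried into the CFU sensitivity analyses too, so they do not guard against it. The time-to-positivity and LAM analyses are unaffected, but they carry no formal success criteria.

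**Working it through.** **Inputs.** From SAP 11.1.1: the 401-colony threshold, the substitute of 401 CFU/mL, and the divisor 0.909 × 0.2 = 0.1818. From SAP 6.2: N = 15 per group, SD 0.1, and a detectable mean reduction of 0.067 (0.079) per day. Assumed: the dilution factor is 1 for undiluted plates and 10^-k otherwise.

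**The plan's own figure.** The plan gives no figure for the effect of this rule. The power statement used below for scale does reproduce: a one-sample, one-sided t test with 14 degrees of freedom gives 79.4% (89.7%) against the stated 80% (90%). It does not depend on the TNTC rule.

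**Size of the shortfall.** The value entered is log10(401) = 2.603 at every dilution. The lower bound is 401 / (d × 0.1818):

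| Dilution factor d | CFU/mL | log10 | Shortfall g |
|---|---|---|---|
| 1 | 2,206 | 3.344 | 0.74 |
| 10^-1 | 22,057 | 4.344 | 1.74 |
| 10^-2 | 220,572 | 5.344 | 2.74 |
| 10^-3 | 2,205,721 | 6.344 | 3.74 |

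This takes the mean of the two plates to be at least 401. The SAP does not say whether one TNTC plate is enough to label the sample. If it is, the smallest shortfall is 0.44 (plates of 401 and 0: 200.5 / 0.1818 = 1,103 CFU/mL, or 3.043 log10).

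**Rank order.** 401 × 0.1818 = 72.9, so 401 CFU/mL corresponds to about 73 colonies undiluted. Countable undiluted samples above that, up to 400 colonies (2,200 CFU/mL), rank above a TNTC sample.

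**Effect on one participant, linear fit.** Over t = 0 to 14 the mean day is 7 and the sum of (t - 7)² is 280. A value entered g too low on day t shifts the slope by g × (7 - t)/280.
- Both screening samples TNTC (t = 0): 0.74 × 7/280 = +0.019; 3.74 × 7/280 = +0.094. With only one of the two TNTC, half of that.
- Day 14 TNTC: -0.019 and -0.094.
- Day 7 TNTC: 0.

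**Effect on a group of 15.** One such participant moves the mean by 0.0185/15 = 0.001, or by 0.0935/15 = 0.006 at 10^-3. The planning standard error is 0.1/√15 = 0.026, so this is about 0.05 to 0.24 standard errors.

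**When the bilinear model is chosen.** The linear figure is not an upper limit. In simulated flat profiles at 4 log10 (residual SD 0.3, assumed) with only the screening value replaced by 2.603, the AIC-selected mean was +0.098. The linear formula gives 1.397 × 7/280 = 0.035. Most of the gap is taken up by a steep first segment, and the result is close to 1.397/14 = 0.100.

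**Average-change sensitivity analysis.** The shift is g/14: 0.74/14 = 0.053 and 3.74/14 = 0.267, positive for baseline and negative for Day 14. It arises only if the baseline or the last value is TNTC.

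**Illustrations only.** These simulations follow the SAP's AIC selection with one plated dilution, a common baseline, between-participant slope SD 0.05 to 0.08 (in SAP 6.2 "standard deviations associated with BAcfu(0-14) were relatively consistent across 5 treatment groups, ranging from 0.05 to 0.08") and residual SD 0.22 to 0.55. For undiluted plates:
- Zero effect, baseline 0.3 to 1.0 log10 below the limit: mean slope -0.042 to -0.007.
- True mean -0.067, baseline at the limit: -0.057 to -0.041.
- With the converted value, the same two settings give -0.023 to -0.001 and -0.072 to -0.058 over all dilutions.
- True mean -0.067, baseline 1.5 to 2.0 below the limit: -0.076 to -0.066 over all four dilutions, which is little bias. A zero-effect group there gives -0.042 to 0.000, with the worst cases at 10^-3.

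**The case against.** The strongest reply is that this is a labelling slip. Threshold and substitute are the same number, which fits a plate-count cap applied before conversion. SAP 11.1.1 is loose with units elsewhere, and the code in Appendix 4 takes the log count as given, so nothing in the documents implements the literal reading. That may well be the intent, but the sentence does not say it. The neighbouring floor of 5 makes sense only in CFU/mL, since one colony undiluted is 1/0.1818 = 5.5 CFU/mL. A programmer following the text would code 401 CFU/mL, and no other section converts or censors the value.

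The second reply is that materiality is not shown. This stands. A dilution term in the formula suggests that diluted samples are plated, in which case TNTC samples may be rare. A single affected participant moves a group mean by a small fraction of its standard error in the linear fit. The simulations that show large effects place baselines at or near the limit, and most undiluted and 10^-1 settings lie below the intercept range that the SAP's own code searches.

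Third, the shortfalls beyond 0.74 need a dilution factor written as a fraction. That is the natural reading but remains an assumption.

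**Conclusion.** The rule is on the wrong scale as written, and it gives a wrong primary-endpoint value whenever it is used. The shortfall is 0.74 log10 for undiluted plates with a mean count of 401, and larger for higher counts. On the fractional-dilution assumption each tenfold dilution adds 1.0. In a linear fit the participant's slope moves by 0.019 per day at most for g = 0.74, positive for screening and negative for Day 14. The shift can be larger where the bilinear model is selected.

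A reader might go further and infer that the trial's primary result is materially biased, or biased in one direction. The documents do not support that: TNTC frequency and plated dilutions are not given, the sign depends on the day, and the net effect may be small. Nor should the starting grid in Appendix 4, "parms alpha=4 to 8 by 0.5", be read as showing that real shortfalls run from 1.40 (4 - 2.60) to 5.40 (8 - 2.60). Those are starting values for a fitting routine, not predicted counts.

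It should still be corrected. The error sits in the primary endpoint, and sponsor and CRO staff are open label, so a choice between the two readings should not be left until data have been seen.

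**What to change.** Replace the TNTC rule in SAP 11.1.1 with:

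> CFU/mL is calculated from the countable dilution where there is one. Only if a sample is TNTC at every dilution plated, the count of each TNTC plate is set to 401 at the highest dilution plated, and CFU/mL is then calculated with the formula above.

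Also state that the dilution factor is a fraction, with 1 meaning undiluted. The restriction to samples TNTC at every dilution matters; without it, a crowded low-dilution plate could override a countable plate at a higher dilution. Setting the count per plate covers the case of one TNTC plate: 401 and 300 undiluted average 350.5, which gives 1,928 CFU/mL (3.29 log10).

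The cost is small: a short change to the SAP text and no new data, because the formula already needs the dilution factor. If TNTC never occurs, nothing changes. The converted value is still a lower bound, so some truncation remains. A sensitivity analysis that treats it as right-censored is optional and not part of the correction.

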9.4.1. Bactericidal Activity Analyses

9.4.1.1. Primary Bactericidal Activity Analyses

The primary endpoint will be the slope of the log CFU counts from screening to Day 14 [$BA_{CFU}(0-14)$], i.e., average change in log CFU count per day over 14 days, where sputum is collected twice during the screening phase and daily thereafter. The \log_{10} CFU counts vs. time profiles over 14 days of treatment may be biphasic, i.e. the rate of change in \log_{10} CFU changes over time. A simple solution³ is to characterize the subject-specific \log_{10} CFU count vs. time profiles using a bilinear regression model, which has been proved to fit the data of many TB bactericidal agents quite well, especially over the time interval of 14 days. However, it is also likely that the some of the subject-specific \log_{10} CFU count vs. time profiles will be better characterized using a simple linear regression model.

The average slope can be estimated for each subject, i , as the mean of the slopes over each day, i.e.,

$$BA_{CFU}(0-14)_i = \sum_{t=1}^{14} \hat{\beta}_{it} / 14,$$

where $\hat{\beta}_{it}$ is the estimated slope for subject i at time t . For each subject, slopes will be estimated using both bilinear and simple linear regression models, and the better fit model (based on lower AIC) will be selected for that subject. The log CFU screening measurement used in the model will be the average of the two individual screening measurements. If the bilinear regression model is selected, the average change in \log_{10} CFU per day over 14 days will be estimated by:

$$BA_{CFU}(0-14)_i = \sum_{t=1}^{14} [\hat{\beta}_{1i} I(t \leq \hat{\kappa}_i) + \hat{\beta}_{2i} I(t > \hat{\kappa}_i)] / 14,$$

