8 CHANGES IN CONDUCT / RE-LANNED ANALYSES FROM THE PROTOCOL

No changes have been made to the planned analyses.

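### The SAP's printed formula for the bilinear primary endpoint when Day 14 is missing drops kappa from the first slope, contradicting its own 14-day formula and Appendix 4 code

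*SAP*

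**What the plan says.** Below, b1 and b2 are the slopes before and after the node kappa, and t_last is the last day with an observed CFU.

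- **SAP 11.1.1, Day 14 present:** "BA_{CFU}(0-14)_i = [\hat{\kappa}_i \hat{\beta}_{1i} + (14 - \hat{\kappa}_i) \hat{\beta}_{2i}] / 14". Here kappa multiplies b1.
- **SAP 11.1.1, Day 14 missing:** "BA_{CFU}(0 - t_{last})_i = [\hat{\beta}_{1i} + (t_{last} - \hat{\kappa}_i) \hat{\beta}_{2i}] / t_{last". In the right-hand side, "\beta}_{1i} + (t_{last} - \hat{\kappa}_i) \hat{\beta}_{2i}] / t_{last", nothing multiplies b1.
- **SAP Appendix 4, bilinear model with kappa estimated:** the estimate statement begins "estimate 'BACfu(0-14)' (kappa*betal + (t_last", then subtracts kappa, multiplies by b2 and divides by t_last. It serves participants with and without a Day 14 value, and kappa is on the first slope (printed there as betal).
- **Protocol 9.4.1.1:** the endpoint is the mean of the daily slopes, written as a sum over days 1 to 14 of "\beta}_{1i} I(t \leq \hat{\kappa}_i) + \hat{\beta}_{2i} I(t > \hat{\kappa}_i)] / 14". The first slope is counted once for each whole day up to kappa.
- **SAP Section 8:** "No changes have been made to the planned analyses". The Amendment 2 entry in SAP Appendix 5 nevertheless records a refined definition of the bilinear endpoint.

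SAP 11.1.1 bounds kappa strictly between 1 and 14 and lets AIC choose between the linear and bilinear fits for each participant. If the linear model wins, the endpoint is simply the fitted slope.

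**The concern.** The endpoint is an average daily change, so each slope must be weighted by the number of days it covers. In the missing-Day-14 formula, b1 gets a weight of one day whatever kappa is. The units show the slip: b1 is log10 CFU per day, while (t_last - kappa)*b2 is log10 CFU, and the two cannot be added.

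The rule belongs to the primary endpoint and can be expected to apply. SAP 11.1.1 sets contaminated or no-result samples to missing, SAP 9.4.3 imputes nothing, and the mITT population keeps everyone who took at least one dose. Two programmers, one working from the text and one from the appendix, would get different primary values for the same participant. The values feed the ANCOVA and the step-down test, where a failed cohort stops formal testing of the lower dose groups.

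**Working it through.** Signs follow the Appendix 4 code: a negative slope means killing.

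**1. The plan's own figure.** SAP 6.2 gives N = 15, SD 0.1, one-sided 5%, and 80% (90%) power at a reduction of 0.067 (0.079). With a one-sample t test on 14 df, the noncentrality is 0.067*sqrt(15)/0.1 = 2.59 and 0.079*sqrt(15)/0.1 = 3.06. Power is 79.4% and 89.7%. The figure reproduces and is not in dispute; it serves as a yardstick in step 6.

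**2. What the formula should return.** The fitted curve starts at alpha and, for kappa <= t_last, ends at alpha + kappa*b1 + (t_last - kappa)*b2. The average daily change is therefore [kappa*b1 + (t_last - kappa)*b2]/t_last. This is the Appendix 4 expression, and at t_last = 14 it is the SAP's 14-day formula. If kappa were at or beyond t_last, the bilinear fit would be a straight line over the observed days. It would have the same likelihood as the linear fit with two more parameters, so its AIC would be 4 higher and the linear model would be chosen.

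**3. Error of the printed formula.** Printed minus correct = -(kappa - 1)*b1/t_last. The printed weights sum to (1 + t_last - kappa)/t_last, which equals 1 only at kappa = 1, a value the SAP's bounds exclude.

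**4. Consistency at t_last = 14.** With b1 = -0.20, b2 = -0.06, kappa = 3:
- 14-day formula and code: (-0.60 - 0.66)/14 = -0.0900
- printed missing-Day-14 form: (-0.20 - 0.66)/14 = -0.0614

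**5. Single participants.** All parameter values are assumed; t_last = 13.

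| b1 | b2 | kappa | Correct | Printed |
|---|---|---|---|---|
| -0.30 | -0.05 | 4 | -1.65/13 = -0.127 | -0.75/13 = -0.058 |
| -0.15 | -0.05 | 5 | -1.15/13 = -0.088 | -0.55/13 = -0.042 |
| +0.05 | -0.12 | 4 | -0.88/13 = -0.068 | -1.03/13 = -0.079 |

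In the first two rows the printed value is too close to zero. In the third, where the first slope is a rise, it overstates killing.

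**6. Group mean.** Taking the second row, the error per affected participant is 4*0.15/13 = 0.046. The documents do not say how many participants would be affected, so a range of 1 to 3 of 15 is assumed, with the SD held at 0.1.

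| Affected of 15 | Shift of group mean toward zero | Power at 0.067 |
|---|---|---|
| 0 | 0 | 79% |
| 1 | 0.003 | about 76% |
| 2 | 0.006 | about 72% |
| 3 | 0.009 | about 69% |

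**7. Protocol sum against SAP formula, Day 14 present.** The protocol's sum equals [floor(kappa)*b1 + (14 - floor(kappa))*b2]/14, so the two differ whenever kappa is not a whole number and the slopes differ. With assumed b1 = -0.30, b2 = -0.03, kappa = 2.9:
- protocol: (-0.60 - 0.36)/14 = -0.069
- SAP: (-0.87 - 0.333)/14 = -0.086

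The gap is 20% of the SAP value. It comes from a tenfold slope ratio and a kappa just short of a whole day, so it is near the top of what rounding down can do.

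**The case against.** **The code is already right.** SAP 9.1 names the Appendix 4 code as what will be used for the efficacy analyses, and SAP 11.1.1 says the endpoint can be estimated directly in PROC NLMIXED. This stands. A reader might infer that the planned primary analysis is biased; the documents do not support that, because bias arises only if the text formula is programmed.

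**The omission may come from PDF reading.** The supplied SAP text is damaged elsewhere: the Section 8 heading is garbled, and the multiplicity method in 11.1.1 is misspelled against the protocol. This also stands as a caution. Kappa does survive in the second term of the same formula and in the 14-day formula, but only the source page can settle it.

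**The reach is narrow.** A reader might infer that every early withdrawal and every contaminated Day 14 sample is affected. That is not so: the bilinear model must also win on AIC. Nor does a straight-line profile show the effect in practice, since equal slopes leave the bilinear AIC 4 higher and the linear model is used.

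**The direction is not fixed.** A reader might infer that killing is always understated. SAP 11.1.1 describes both slopes as declines, but the fitted slopes are not constrained in sign, and a rising first slope reverses the error.

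**The protocol difference is logged.** SAP Appendix 5 notes the refined definition, and Protocol 10.1.7 lets the SAP carry modifications to the analyses. A reader might infer that the protocol must be amended; these passages show otherwise. What remains is that SAP Section 8, where such a change is declared, says there is none.

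None of this makes the printed formula correct. It is a stated rule for the primary endpoint, and it conflicts with the formula just above it and with the code.

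**Conclusion.** In the supplied text, the missing-Day-14 formula in SAP 11.1.1 is wrong as written. The algebra rests on no assumption: the error is (kappa - 1)*|b1|/t_last for a participant with the bilinear model selected and no Day 14 CFU. For one such participant it can be large, halving the value or more in the first two assumed examples. At group level it is modest in the scenario tried, about 0.003 to 0.009 for 1 to 3 affected of 15, against a design effect of 0.067. The participant and group sizes rest on assumed slopes, kappa, t_last and numbers affected, because the documents give none of these. The finding is conditional on kappa being absent from the source page, and it changes results only if the text rather than the code is programmed. The protocol's whole-day sum and the SAP's continuous kappa do differ, but this is a matter of declaring the change.

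**What to change.** 1. Check the source page of SAP 11.1.1. If kappa is absent, write BA(0-t_last) = [kappa*b1 + (t_last - kappa)*b2]/t_last, so that the text matches Appendix 4 and reduces to the 14-day formula at t_last = 14.
2. In SAP Section 8, state that the bilinear endpoint uses continuous kappa in place of the protocol's whole-day indicator sum, with a cross-reference to the Amendment 2 entry in Appendix 5.

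The cost is one symbol and one sentence in the SAP. No new data, code change or protocol amendment is needed.
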